8.2. Safety assessments

The investigator and his/her designees are responsible for detecting, documenting, and reporting events that meet the definition of an AE or SAE. The investigator and designees are responsible for following up AEs that are serious, considered related to the study intervention or the study, or that caused the participant's withdrawal from the study interventions.

8.2.1. Pre-vaccination procedures

8.2.1.1. Collection of demographic data

Record demographic data such as year of birth, sex, race* and ethnicity* in the participant's eCRF.

*Differences in the safety and efficacy of certain medical products, including vaccines [[Haralambieva](#), 2013; [Pérez-Losada](#), 2009; [Kollmann](#), 2013] have been observed in racially and ethnically distinct subgroups. These differences may be attributable to intrinsic factors (e.g., genetics, metabolism, elimination), extrinsic factors (e.g., diet, environmental exposure, sociocultural issues), or interactions between these factors. Therefore, both geographic ancestry (race) and ethnicity will be collected for all study participants.

8.2.1.2. Medical history

Obtain the participant's medical history by interviewing the participant and/or review of the participant's medical records. Record any relevant pre-existing conditions, signs and/or symptoms present prior to the study intervention in the eCRF.

8.2.1.3. Vaccination history

Obtain the participant's vaccination history by interviewing the participant and/or review of the participant's vaccination records.

Any vaccine administered up to 1 year before study vaccine administration should be recorded in the eCRF with date of vaccination. Any FLU vaccine administered up to 3 years before study intervention should be recorded with the date of vaccination and information about the vaccine formulation (e.g., adjuvanted or non-adjuvanted or high-dose).

8.2.1.4. History directed physical examination

- History directed physical examination will be performed for each participant.
- If the investigator determines that the participant's health on the day of study intervention administration temporarily precludes dosing, the visit will be rescheduled. Refer to Section [5.5](#) for the list of criteria for temporary delay of study intervention administration.
- Treatment of any abnormality observed during this examination has to be performed according to local medical practice outside this study or by referral to an appropriate health care provider.

8.2.1.5. Warnings and precautions to vaccination

Warnings and precautions to administration of study intervention must be checked at each visit with planned administration of study intervention.

8.2.1.6. Pre-vaccination body temperature

The body temperature of each participant needs to be measured prior to any study intervention administration and recorded in the eCRF. The route for measuring temperature can be oral *or* axillary. If the participant has fever (fever is defined as temperature $\geq 38.0^{\circ}\text{C}/100.4^{\circ}\text{F}$ regardless the location of measurement) on the day of vaccination, the vaccination visit will be rescheduled within the allowed interval for this visit, refer to [Table 3](#) and [Table 4](#).

8.2.2. Post-vaccination procedures

8.2.2.1. Safety contact at 6 months post-last vaccination

Six months after the last dose of study intervention (i.e. Month 6 for participants in the Co-Ad group and Month 7 for participants of the Control group), each participant should be contacted to check if he/she has experienced any SAEs or any pIMDs since last study intervention administration, and to collect information on concomitant medications/vaccinations.

Multiple formats can be proposed by the site staff to organize these contacts. This contact may be done via email, text message, fax, or phone call for example. The most appropriate format should be agreed between site staff and the study participant.

Text messages, email and fax may be used as a screening to check if the participant has anything to report. If the participant answers "Yes" for at least one of the items of interest, a phone call must be done to get the details on the event(s).

Data collected via phone calls and text messages will have to be recorded in source documents. E-mails and faxes can be archived in source documents. Receipt of the message must be confirmed by the participant or caregiver, as applicable.

8.3. Adverse Events (AEs), Serious Adverse Events (SAEs) and other safety reporting

8.3.1. Time period and frequency for collecting AE, SAE and other safety information

Table 12 Timeframes for collecting and reporting of safety information

Co-Ad group		Pre-Dose*	Vacc Co-Ad	6 months post-last dose** Study conclusion		
Event		D1	D4	D31		
Administration site and systemic solicited events						
Unsolicited AEs						
Control group						
	Pre-Dose*	Vacc FLU		Vacc RSV		6 months post-last dose** Study conclusion
	D1	D4	D31	D31	D34	D61
Administration site and systemic solicited events						
Unsolicited AEs						
All participants						
All SAEs						
All pIMDs						
SAEs related to study participation or concurrent GSK medication/ vaccine						
AEs/SAEs leading to withdrawal from the study						
Intercurrent medical conditions						

D: day; AE: adverse event; SAE: serious adverse event; pIMD: potential immune-mediated disease; Vacc: Vaccination.
* i.e. consent obtained on Day 1 (prior to intervention administration).

** post-last dose= 6 months after Co-Ad vaccine administration (Co-Ad group) or 6 months after RSV investigational vaccine administration (Control group).

Note: COVID-19 cases will be collected during the same timeframes as those used for collecting and reporting the other safety information (unsolicited AEs/SAEs, etc.)

The investigator or designee will record and immediately report all SAEs to the sponsor or designee via the Expedited AE Reporting Form. Reporting should, under no circumstances, occur later than 24 hours after the investigator becomes aware of an SAE, as indicated in Section 10.3.9. The investigator will submit any updated SAE data to the sponsor within 24 hours of it being available.

A post-study AE/SAE is defined as any event that occurs outside of the AE/SAE reporting periods defined in [Table 12](#). Investigators are not obligated to actively seek AEs or SAEs from former study participants. However, if the investigator learns of any SAE, including a death, at any time after a participant has been discharged from the study, and he/she considers the event to be reasonably related to the study intervention, the investigator will promptly notify the study contact for reporting SAEs mentioned in the [Table 14](#).

8.3.2. Method of detecting AEs, SAEs, and other events

Detection and recording of AE/SAE/pIMDs are detailed in Section [10.3.7](#).

Assessment of AE/SAE intensity, causality and outcome are described in Section [10.3.8](#).

Open-ended and non-leading verbal questioning of participants is the preferred method of acquiring information related to an AE/SAE/pIMD.

8.3.3. Regulatory reporting requirements for SAEs and other events

Once an investigator (or designee) becomes aware that a study participant has experienced an SAE/pIMD, it must be reported to GSK using the required documentation and within the timeframes mentioned in [Table 13](#). This is essential for meeting GSK legal obligations and ethical responsibilities for participant safety and the safety of a study intervention under clinical investigation.

For SAEs/pIMDs, the investigator must always provide an assessment of causality at the time of the initial report, as defined in the Section [10.3.8.2](#).

Local regulatory requirements and sponsor policy for preparation of an investigator safety report of Suspected Unexpected Serious Adverse Reactions (SUSAR) must be followed. These reports will be forwarded to investigators as necessary.

The sponsor has the legal responsibility to notify local authorities/regulatory agencies about the safety of an investigational study intervention. The sponsor will comply with country-specific regulatory requirements related to safety reporting to the regulatory authority, IRB/IEC and investigators.

Please refer to the Section [10.3.9](#) for further details regarding the reporting of SAEs/pIMDs.

Table 13 Timeframes for submitting SAE and other events reports to GSK

Type of Event	Initial Reports		Follow-up of Relevant Information on a Previous Report	
	Timeframe	Documents	Timeframe	Documents
SAEs	24 hours*, #	electronic Expedited Adverse Events Report	24 hours*	electronic Expedited Adverse Events Report
pIMDs	24 hours** .#	electronic Expedited Adverse Events Report	24 hours*	electronic Expedited Adverse Events Report

* Timeframe allowed after receipt or awareness of the information by the investigator/site staff.

**Timeframe allowed once the investigator determines that the event meets the protocol definition of a pIMD.

The investigator will be required to confirm review of the SAE/pIMD causality by ticking the 'reviewed' box in the electronic Expedited Adverse Events Report within 72 hours of submission of the SAE/pIMD.

8.3.4. Treatment of AEs

Any medication, vaccine or products which may explain/cause/be used to treat an SAE/pIMD should be recorded in the Expedited Adverse Event Report of the participant's eCRF screen (refer to the Section 10.3.9.1).

8.3.5. Participant card

The investigator (or designee) must provide the participant with a "participant card" containing information about the clinical study. The participant must be instructed to always keep the participant card in his/her/their possession for the duration of the study. In an emergency, this card serves to inform the responsible attending physician/caregiver/family member that the participant is in a clinical study and that relevant information may be obtained by contacting the investigator or his/her back up.

8.4. Pharmacokinetics

Pharmacokinetics are not evaluated in this study.

8.5. Genetics

Genetics are not evaluated in the current study.

8.6. Biomarkers

Not applicable for this study.

8.7. Immunogenicity

Immunogenicity is described in Section 8.1.

8.8. Health outcomes

Not applicable for this study.

9. STATISTICAL CONSIDERATIONS

9.1. Statistical hypotheses (amended 16 December 2022)

Statistical hypotheses are associated to the confirmatory primary non-inferiority (NI) objectives, which will be tested sequentially to control overall Type I error.

Global type I error is controlled at 2.5% (1-sided).

The non-inferiority margins associated to each objective are provided in Table 15.

Table 15 Study objectives and null hypothesis

Objectives	Null hypothesis
Primary	

 To demonstrate the non-inferiority of RSVPreF3 OA investigational vaccine in terms of RSV-A neutralization antibodies when co-administered with the FLU vaccine compared to RSVPreF3 OA investigational vaccine administered alone. 	
 True Group GMT ratio between RSVPreF3 OA investigational vaccine (Control group) divided by RSVPreF3 OA investigational vaccine when co-administered with the FLU vaccine (Co-Ad group) in RSV-A neutralization antibody titers 1 month after the RSVPreF3 OA investigational vaccine dose is above 1.5.

 To demonstrate the non-inferiority of FLU vaccine when co-administered with the RSVPreF3 OA investigational vaccine compared to FLU vaccine administered alone. 	
 True Group GMT ratio between FLU vaccine (Control group) divided by RSVPreF3 OA investigational vaccine when co-administered with the FLU vaccine (Co-Ad group) in HI antibody titers for each of the FLU vaccine strains 1 month after the FLU vaccine is above 1.5.

 To demonstrate the non-inferiority of RSVPreF3 OA investigational vaccine in terms of RSV-B neutralization antibodies when co-administered with the FLU vaccine compared to RSVPreF3 OA investigational vaccine administered alone. 	
 True Group GMT ratio between RSVPreF3 OA investigational vaccine (Control group) divided by RSVPreF3 OA investigational vaccine when co-administered with the FLU vaccine (Co-Ad group) in RSV-B neutralization antibody titers 1 month after the RSVPreF3 OA investigational vaccine dose is above 1.5.

FLU vaccine is referring to FLU HD quadrivalent; HI: Hemagglutinin Inhibition; GMT: Geometric Mean Titer.

Statistical testing of each endpoint will be organized sequentially to control overall Type I error.

9.2. Sample size determination (amended 16 December 2022)

The target enrolment will be 1028 participants (514 in the group receiving the RSVPreF3 OA investigational vaccine co-administered with the FLU vaccine (Co-Ad group) and 514 in the Control group where RSVPreF3 OA investigational vaccine and FLU vaccine are administered staggered) to obtain at least 924 evaluable participants (462 in the Co-Ad group and 462 in Control group) for the evaluation of the ***primary objectives***, assuming that approximately 10% of the enrolled participants will not be evaluable.

Table 16 Overall power to demonstrate primary objectives: non-inferiority of the immunogenicity of RSVPreF3 OA investigational vaccine when co-administered with FLU vaccine as compared to when administered alone- assuming 462 participants are available in each group.

Endpoint	Standard deviation of \log_{10} concentration	Reference ratio	Non-inferiority margin	Type II error	Power
RSV-A Non-inferiority* (1-sided test with alpha = 2.5%)					
GMTs RSV-A neutralization antibody	0.45	1.05	1.5	0.1%	99.9%
FLU Non-inferiority* (1-sided test with alpha=2.5%)					
GMTs HI H1N1 strain	0.6	1.05	1.5	2.5%	97.5%
GMTs HI H3N2 strain	0.6	1.05	1.5	2.5%	97.5%
GMTs HI B/Yamagata	0.6	1.05	1.5	2.5%	97.5%
GMTs HI B/Victoria strain	0.6	1.05	1.5	2.5%	97.5%
RSV-B Non-inferiority* (1-sided test with alpha = 2.5%)					
GMTs RSV-B neutralization antibody	0.45	1.05	1.5	0.1%	99.9%
Global Type II error to show non-inferiority				~10.0%	
Global power					~90.0%

* Pass 2019 alpha = 2.5%, Two-Sample T-Tests for Non-Inferiority Assuming Equal Variance and Equal mean

For RSV: non-inferiority limit = 0.176 ($=\log_{10}[1.5]$).

For each Flu vaccine strain: non-inferiority limit = 0.176 ($=\log_{10}[1.5]$).

Reference Ratio= 0.0212 ($=\log_{10}[1.05]$)

Considering a slight interference of 1.05 in true GMTs in both groups with a common population standard error of 0.45 for the RSV-A **and RSV-B neutralization antibodies** and 0.6 for each of the FLU strains in \log_{10} transformed concentration, the study has at least 90.0% power to meet the ***primary objectives***.

Nominal powers to evaluate secondary objective

The nominal power to evaluate the non-inferiority on seroconversion rate for each of the FLU strains is above 86%, depending on the plausible rates.

Table 17 Evaluation of non-inferiority in terms of HI antibody SCR when the FLU vaccine is co-administered with the RSVPreF3 OA investigational vaccine as compared to FLU when administered alone assuming 462 participants are available in each group for a range of plausible SCRs.

N evaluable participants per group	Threshold	Plausible rates in Control group**	Type II error	Nominal power
FLU vaccine: Non-inferiority* in terms of SCR				
462	10%	70%	8.7%	91.3%
462	10%	50%	13.9%	86.1%
462	10%	35%	11.0%	89.0%
462	10%	25%	6.1%	93.9%

SCR: Seroconversion Rate.

*Pass 2019 alpha = 2.5%, for SCR – Non-inferiority: Proportions – Two independent Proportions – Non-Inferiority Tests for the Difference Between Two Proportions.

** SCR observed in the Control group in Zoster-004 study range from 35.3% to 60.9%.

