9.4.2. Secondary endpoints

- Method for evaluation of non-inferiority of FLU vaccine in terms of HI seroconversion rate for each of the FLU vaccine strains at 1 month after the FLU vaccine (i.e. at Day 31 for both groups):
 - The 2-sided 95% CI on group difference in seroconversion rate (Control group minus Co-Ad group) will be computed based on the method of Miettinen and Nurminen [[Miettinen](#), 1985].
 - Reference criteria for evaluation of non-inferiority: The upper limit of the 2-sided 95% CI on the group difference (Control group minus Co-Ad group) in seroconversion rate is $\leq 10\%$ for anti-HI antibodies.
- The other secondary endpoints are described in Section 3. Descriptive analyses of demography, immunogenicity and safety will be detailed in the SAP.

Table 19 Definitions of seroconversion rate, seroprotection rate and mean geometric increase

Abbreviation/term	Definition
HI SCR/ seroconversion rate	The percentage of vaccinees who have either a HI pre-dose titer $< 1:10$ and a post-dose titer $\geq 1:40$ or a pre-dose titer $\geq 1:10$ and at least a four-fold increase in post-dose titer.
HI SPR/ seroprotection rate	The percentage of vaccinees with a serum HI titer $\geq 1:40$ that usually is accepted as indicating protection.
MGI/ mean geometric increase	The geometric mean of the within participant ratios of the post-dose titer over the pre-dose titer.

- Additionally, the CBER and CHMP criteria for HI SPR and SCR will be assessed as follows:

CBER's criteria:

- The lower limit (LL) of the 95% CI for SCR should be $\geq 30\%$ in participants ≥ 65 YOA.
- The LL of the 95% CI for SPR should be $\geq 60\%$ in participants ≥ 65 YOA.

CHMP's criteria:

At least one of the 3 following criteria should be met:

- the point estimates of SPR $>60\%$, SCR $>30\%$, and MGI >2.0 for elderly ≥ 60 YOA for each of the antigen strains.

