10.6. Appendix 6: Protocol amendment history

The Protocol Amendment Summary of Changes Table for the current amendment is located directly before the Table of Contents (TOC).

DOCUMENT HISTORY	
Document	Date of Issue
Original protocol	20 May 2021
Protocol Amendment 1	8 March 2022
Protocol Amendment 2	16 December 2022

Overall rationale for amendment 1:

The original protocol dated 20 May 2021 was amended on 8 Mar 2022 to update the planned intervals between study visits, remove any mention of European participating sites and related text, evaluate the RSV-B neutralizing antibody titers on the full cohort instead of a subset, simplify the minimization factors to only age and center, include a Screen Failure data collection section, replace the vaccine Flu recommended strains for the 2021-2022 season for the ones recommended for 2022-2023 season, increase the sample size for the study, and update the list of pIMDs. Additionally, other administrative and editorial changes were made.

Summary of Changes Table for Amendment 1

Section # and title	Description of change	Brief rationale
Table 3 Intervals between study visits (Co-Ad group) Table 4 Intervals between study visits (Control group)	Updated the allowed interval range from 30 to 42 days to 30 to 37 days between Visit 1 and Visit 2 for the Co-Ad group and between Visit 1 and Visit 2 and Visit 2 and Visit 3 for the Control group.	Alignment with project requirements.
Section 2.1 Study rationale Section 4.1.1 Overview of recruitment plan Section 8 STUDY ASSESSMENTS AND PROCEDURES	Updated the text pertaining to the participating countries to delete mention of European sites and related information.	Change following feasibility exercise and project strategy.
Section 3 OBJECTIVES AND ENDPOINTS Section 6.3.4 Allocation of participants to assay subsets Section 8.1.3 Immunological read-outs	Updated to indicate RSV-B neutralizing antibody tests on the full population and not a subset.	To obtain data from a larger sample size.
Table 6 Study groups and intervention Table 11 Immunological Read-outs Section 9.2 Sample size determination	Increased the study sample size from a total of 880 participants (440 in each group) to 1028 participants (514 in each group).	To consider a slight interference of 1.05 in true geometric mean titers (GMTs) in both groups.

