4.3.1.1. Between groups assessment

- The asymptotic standardized 95% CI for the difference in seroconversion rate (Control group minus Co-Ad group) will be computed at 1 month after the FLU vaccine (i.e. at Day 31 [Visit 2] for both groups).

Reference criteria for evaluation of non-inferiority:

The upper limit of the 2-sided 95% CI on the group difference (Control group minus Co-Ad group) in seroconversion rate is $\leq 10\%$ for anti-HI antibodies.

The between groups analysis of secondary endpoints presented in this section will be descriptive with the aim to characterize the difference in immunogenicity between groups. These descriptive analysis should be interpreted with caution considering that there is no adjustment for multiplicity for these comparisons.

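### Must the seroconversion power carry the same interference allowance as the GMT power beside it?

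*Protocol*

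**What the plan says.** Protocol 9.2 and SAP 5 each contain two power calculations, both at 462 evaluable participants per group.

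- **Primary (Protocol Table 16, SAP Table 2).** GMT non-inferiority against a margin of 1.5. The text sets a true ratio that favours Control: "Considering a slight interference of 1.05 in true GMTs in both groups". The table has a reference-ratio column showing 1.05, and a note gives its log10 value, 0.0212. The software footnote under the same table reads "Two-Sample T-Tests for Non-Inferiority Assuming Equal Variance and Equal mean".
- **Secondary (Protocol Table 17, SAP Table 3).** SCR non-inferiority against a 10-point limit. The rate column is headed "Plausible rates in Control group", and no Co-Ad rate or true difference appears. A footnote gives the background: "SCR observed in the Control group in Zoster-004 study range from 35.3% to 60.9"%. The accompanying sentence is "The nominal power to evaluate the non-inferiority on seroconversion rate for each of the FLU strains is above 86%, depending on the plausible rates".

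The history of Amendment 1 (Protocol 10.6) explains the rise in enrolment from 880 to 1028: "To consider a slight interference of 1.05 in true geometric mean titers (GMTs) in both groups". SAP 4.3.1.1 gives the status of the SCR comparison: "The between groups analysis of secondary endpoints presented in this section will be descriptive". It adds that there is no multiplicity adjustment.

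**The concern.** SCR is computed from the same Day 31 HI titers as the influenza GMT ratio. For a participant with a measurable baseline it requires "at least a four-fold increase in post-dose titer" (Protocol Table 19). If co-administration lowers titers a little, some participants near that threshold will no longer seroconvert. The section allows for such a loss when it powers the GMT endpoints, and the loss was the stated reason for enlarging the trial. A few lines later the SCR power appears to assume no loss, and does not say so.

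The only reference to equality, in the software footnote, sits under the GMT table, where the figures do not use it. The SCR table, where the figures do use equality, has no such note.

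The stake would be a reader who trusts a floor of 86% per strain and then misjudges a strain that misses the 10-point criterion.

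**Working it through.** **Inputs.** From Protocol 9.2 and 9.4.2 and SAP 5: n = 462 per group; one-sided alpha 2.5% (z = 1.96); SCR limit 0.10 for Control minus Co-Ad; Control SCR p1 = 0.70, 0.50, 0.35, 0.25; Miettinen-Nurminen method; HI log10 SD 0.6; GMT margin 1.5 (log10 0.1761); GMT ratio 1.05 (log10 0.0212). The true Co-Ad deficit d is not in the documents. The values 0, 1 and 2 points below are assumptions chosen to show sensitivity.

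**Step 1: reproduce the SCR table.** With p2 = p1 − d,

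power ≈ Φ[(0.10 − d)/SE − 1.96], SE = √{[p1(1−p1) + p2(1−p2)]/462}.

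At d = 0:

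| Control SCR | SE | 0.10/SE − 1.96 | Approximate power | Exact Miettinen-Nurminen | Printed |
|---|---|---|---|---|---|
| 70% | 0.03015 | 1.357 | 91.3% | 91.3% | 91.3% |
| 50% | 0.03290 | 1.080 | 86.0% | 86.1% | 86.1% |
| 35% | 0.03138 | 1.227 | 89.0% | 89.0% | 89.0% |
| 25% | 0.02849 | 1.550 | 93.9% | 94.0% | 93.9% |

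The exact column enumerates all 463 × 463 outcomes of the score test. The four printed powers are correct, and they assume d = 0.

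**Step 2: reproduce the GMT power.** SE = 0.6 × √(2/462) = 0.03948.

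- At ratio 1.05: (0.1761 − 0.0212)/0.03948 = 3.924, and Φ(3.924 − 1.96) = 97.5%, the printed value.
- At ratio 1.0: 0.1761/0.03948 = 4.461, and Φ(4.461 − 1.96) = 99.4%.

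So the GMT figures use 1.05. The equal-means phrase in that footnote does not describe them.

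**Step 3: how much slack the SCR floor has.** Exact power:

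| Control SCR | d = 0 | d = 1 point | d = 2 points | Deficit at which power reaches 86% |
|---|---|---|---|---|
| 70% | 91.3% | 84.5% | 75.0% | 0.81 points |
| 50% | 86.1% | 78.3% | 68.4% | 0.02 points |
| 35% | 89.0% | 82.2% | 73.0% | 0.49 points |
| 25% | 94.0% | 88.9% | 81.3% | 1.43 points |

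The dependence on equal rates is real. Across the full set of tabulated rates, the 86% floor holds only if Co-Ad is essentially no lower than Control. That strict form comes from the 50% row; the other three tolerate roughly half a point to a point and a half.

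**Step 4: what depends on this number.**

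- *Enrolment.* Both documents set 462 per group for the primary objectives. Table 16 drives the size and Table 17 does not.
- *Decision rule.* Protocol 9.4.1.1 and SAP 4.2.2 place RSV-A and the four strain GMT ratios first, then RSV-B. SCR is in neither step.
- *Analysis.* The SCR interval and the 10-point reference criterion (Protocol 9.4.2, SAP 4.3.1.1) use the observed data only. No planning power enters them.

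None of these changes with d.

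**The case for a change.** The strongest case for a change is that equality cannot be taken as the default here. The same section departs from equality for the same assay and blood draw, and that departure is why the trial grew. SCR non-inferiority is a listed secondary objective with a numerical criterion, and the sponsor chose to publish a power for it. Calling that power nominal does not disclose the assumed difference. Within the cited range of 35.3 to 60.9%, a deficit of only 0.5 points puts power below 86% at every rate (the maximum is 85.7%, at 35.3%).

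The arithmetic stands, and so does the omission: neither document states the Co-Ad rate. The step from there to an inconsistency is weaker. No statement says the SCR power includes interference, so no two statements conflict. The 1.05 is attached to GMTs and to the primary objectives, while SCR has its own subheading, scale, limit and test. A GMT ratio does not fix an SCR deficit. That needs the SD of the log10 fold rise, which the documents do not give; 0.6 is the SD of the titer. If one assumes an SD of 0.4 to 1.0 and a uniform normal shift, the 50% row falls to between 67 and 80%. That range shows how far the answer depends on the assumption, and the model also ignores the two-fold dilution steps and the two baseline branches of the SCR definition.

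The equal-means footnote is a clerical slip. The column, the note and the text around it all say 1.05, so nobody would be misled about what was computed.

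**Conclusion.** No change follows. The printed SCR powers are correct at equal true rates, which is the ordinary reading of a non-inferiority table with one rate per row and a margin, and a statistician recovers that assumption at once by recomputing any row. The sensitivity is genuine (78.3% at 50% SCR for a 1-point deficit, 68.4% for 2 points), but it concerns a descriptive comparison that sets neither the sample size nor any confirmatory conclusion. A note on the assumption, or a grid of deficits, would be harmless but would alter no enrolment figure, criterion, analysis or result.

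This rests on the SCR comparison staying descriptive, as SAP 4.3.1.1 has it. It also rests on 462 evaluable per group and the Miettinen-Nurminen method. The deficits of 1 and 2 points are illustrative, since the documents give no expected Co-Ad SCR.
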